
Planned Sample Size: The sample size for the study is based on the sample size required to reject the null hypothesis for the primary efficacy endpoint.
 
The number of subjects was estimated based on 2 meta-analysis studies that reviewed 50 and 72 articles respectively (Bonito, 2005) to reach a significant difference in PD reduction at 9 months compared with placebo.
 
Using the normal approximation for sample size determination for 2 independent samples, t-tests, and assuming a PD reduction of 0.5 mm on average (difference in means) with a standard deviation of 0.7 mm, <math>\alpha=0.05</math> (0.025 per comparison), and 85% power, a sample size of 44 per group will be required. The expected dropout rate is 20% based on previous experiments; hence 50 subjects will be enrolled per group. Generalized estimating equations (GEE) analyses will be performed and therefore, the actual power will be between 85 and 90%.

Statistical methods: Analysis of the clinical efficacy data will consist of modeling endpoints, including change from baseline in PD, CAL, BOP, and FMPI, with treatment group as a main effect and adjusting for baseline values of a given endpoint. Post-baseline treatment comparisons will be modeled through a GEE method (with a linear link and exchangeable covariance matrix), adjusting for the baseline value. Methods of analysis for periodontal flora, inflammatory cytokine levels in GCF and in serum, and RBL will be described in separate statistical analysis plans. Results will be considered significant if <math>p < 0.05</math>.

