At each evaluation, medical and dental history will be updated, an oral exam will be performed, and AEs and SAEs will be assessed and recorded. PD, CAL, and BOP will be evaluated at screening and on Days 15, 30, 60, 90, 180, and 270. Subjects will have urinalysis in addition to blood tests including hematology and chemistry (liver and kidney function) panels done at screening and repeated at Days 90 and 270. FMPI will be recorded at baseline and on Days 15, 30, 60, 90, 180, and 270. Inflammatory cytokines in serum will be measured at baseline and on Days 15, 90, 180, and 270. GCF will be collected and analyzed at baseline and on Days 15, 90, 180, and 270. Microbial analysis of periodontal flora will be performed at baseline and on Days 15, 90, 180, and 270.

At each treatment visit, in addition to administration of ST266 or placebo, medical and dental history will be updated, AEs and SAEs will be assessed and recorded, concomitant medications will be recorded, and oral hygiene instruction will be provided.

Randomization will be stratified by site and smoker status (never smoked or quit smoking more than two years ago vs. has smoked within the last two years). Randomization will be blocked such that assignment to treatment groups both within sites and within smoker status will be

approximately even (1:1:1). ST266 will be supplied to the study site and prepared for use by trained clinical staff, who will not be the same as the dental professionals evaluating the subjects.

**Primary Endpoint:** The primary effectiveness endpoint of this study is the average change in PD from baseline to 9 months (Day 270) in tooth-sites with baseline PD  $\geq$  6mm. This endpoint will be analyzed at the patient level similar to other studies.

**Secondary Endpoints:** Secondary efficacy endpoints of this study are: (1) change from baseline in CAL at 9 months (Day 270) with baseline PD  $\geq$  6mm; (2) change from baseline in BOP at 9 months (Day 270) using whole-mouth average, and (3) change from baseline in PD at 9 months (Day 270) using all tooth-sites.

Baseline refers to the initial measurement of the endpoint, which may occur at the screening or baseline visit according to the schedule of assessments.

**Safety Endpoints:** The safety endpoints are frequency and pattern of AEs and SAEs.

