## 7.2. Number of Subjects

One hundred and fifty (150) subjects will be enrolled. The sample size for the study is based on the sample size required to reject the null hypothesis for the primary efficacy endpoint which contains two comparisons. Using the normal approximation for sample size determination for two independent samples, t-tests, and assuming a PD reduction of 0.5 mm on average (difference in means) with a standard deviation of 0.7 mm,  $\alpha=0.05$  (Bonferroni corrected,  $\alpha$  0.025 per comparison), and 85% power, a sample size of 44 per group will be required. The expected dropout rate is 20% based on previous experiments and current enrollment trends hence 50 subjects will be enrolled per group. GEE analyses will be performed and therefore, the actual power will be between 85 and 90%.

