3. GENERAL ANALYSIS AND REPORTING CONVENTIONS

For continuous endpoints, the summary statistics will generally include number of subjects with data (n), mean, standard deviation, median, minimum and maximum. No preliminary rounding will be performed; rounding will only occur after analysis. To round, the digit to right of last significant digit will be considered: if < 5 then round down, if ≥ 5 then round up. Means and medians will be presented with one more decimal place than the precision of the data. Standard deviations will be presented with two more decimal places than the precision of the data. Percentages will be presented with one decimal place. Minimums and maximums will be presented with the same precision as the original data.

For categorical endpoints, the summary statistics will generally include: number of subjects randomized and/or dosed, number of subjects with data, and the percentage of those with data in each category. Frequency distributions will be presented as appropriate.

Analysis of the clinical efficacy data will consist of modeling endpoints, including change from baseline in PD, CAL, BOP, and FMPI, with treatment group, patients, smoking status, and investigational site as main effects and adjusting for baseline values of a given endpoint. Post-baseline treatment comparisons will be modeled through a GEE method (with a linear link and exchangeable covariance matrix), adjusting for the baseline value. Methods of analysis for periodontal flora, inflammatory cytokine levels in GCF and in serum, and RBL will be described in separate statistical analysis plans.

Hypothesis testing, unless otherwise indicated, will be two-sided. When confidence intervals are presented, they will be two-sided with a confidence coefficient of 95%. Actual P-values will be reported to 3 decimal places if greater than 0.001. If less than 0.001, the value ' <0.001 ' will be reported.

The statistical software, SAS[®] version 9.3 or above, will be used for all summaries and statistical analyses.

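### The protocol credits GEE with 85 to 90% power but gives nothing to support it; its own inputs give about 82% with the completers expected at 20% dropout.

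*Protocol*

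**What the plan says.** Protocol 7.2 describes the calculation as "Using the normal approximation for sample size determination for two independent samples, t-tests", "assuming a PD reduction of 0.5 mm on average (difference in means) with a standard deviation of 0.7 mm". Alpha is "0.025 per comparison" after a Bonferroni correction, and the result is "and 85% power, a sample size of 44 per group will be required". It then assumes 20% dropout, enrols 50 per group, and closes with "GEE analyses will be performed and therefore, the actual power will be between 85 and 90" percent. The synopsis, under planned sample size, repeats the closing statement: "analyses will be performed and therefore, the actual power will be between 85 and 90" percent.

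Protocol 7.1 says of the primary endpoint: "This endpoint will be analyzed at the patient level similar to other studies". Protocol 13 describes a GEE with an exchangeable covariance matrix, adjusted for the baseline value. The model code in SAP 8.3.1 adds investigational site, smoking status and the smoking-by-treatment interaction, and restricts the data to Day 270 records.

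SAP 2.6 repeats the t-test sizing with about 10% dropout and the same 50 per group. It does not repeat the statement about GEE and power.

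**The concern.** The wording makes GEE the cause of a power above the t-test figure. An exchangeable GEE on tooth-sites mainly ensures that correlated sites are not counted as independent. Because whole patients are randomised, the treatment contrast is between patients, and the patient mean in the t-test already pools the qualifying sites. With one visit in the primary model, repeated measurements over time add nothing either.

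The sentence comes straight after the dropout step, so a reader takes it as assurance that power stays at 85% or more after losses. If the protocol's inputs do not give that, the stated power is too high for the completer number that the protocol itself expects.

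**Working it through.** **Inputs.** Difference 0.5 mm, SD 0.7 mm, alpha 0.025 per comparison, 85% power, 44 per group (Protocol 7.2). Two-sided testing (SAP 3: "Hypothesis testing, unless otherwise indicated, will be two-sided"). Dropout 20% (Protocol 7.2) or about 10% (SAP 2.6), with 50 enrolled per group in both.

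**1. The plan's own figure.** Normal approximation: n = 2 × [SD × (z₀.₉₈₇₅ + z₀.₈₅) / difference]² = 2 × [0.7 × (2.2414 + 1.0364) / 0.5]² = 42.1, so 43 per group. The noncentral t distribution gives 84.6% at 43 and 85.5% at 44, so 44 is the exact t answer. The stated sample size is reproduced.

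**2. Power by evaluable number, with no GEE gain.** Noncentrality = 0.5 / (0.7 × √(2/n)); for n = 40 this is 0.5 / 0.1565 = 3.194.

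| Evaluable per group | Source | Exact t | Normal approximation |
|---|---|---|---|
| 40 | 50 × 0.80, protocol dropout | 81.6% | 83.0% |
| 44 | sizing target | 85.5% | 86.6% |
| 45 | 50 × 0.90, SAP dropout | 86.4% | 87.4% |
| 50 | all enrolled | 90.0% | 90.8% |

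The range 85 to 90% is therefore the plain t-test power for 44 to 50 patients per group. It does not cover 40.

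**3. What clustering alone adds.** With equal site counts, the exchangeable GEE estimate is the difference in patient means. In simulation at 44 per group (20 sites each, ICC 0.1), both had a standard error of 0.1478. With unequal counts, GEE reweights patients. The documents give no ICC or distribution of site counts, so the ranges below assume a minimum of 6 sites and a mean of 12 to 30. Power is by normal approximation.

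| ICC | Variance reduction | Power at 44 (base 86.6%) | Power at 40 (base 83.0%) |
|---|---|---|---|
| 0.3 to 0.5 | 0.1 to 0.7% | 86.7 to 86.9% | 83.0 to 83.2% |
| 0.2 | 1 to 2% | 87.0 to 87.2% | 83.4 to 83.6% |
| 0.1 | 3 to 5% | 87.7 to 88.4% | 84.2 to 85.0% |
| 0.05 | 6 to 11% | 88.7 to 90.6% | 85.3 to 87.5% |

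The simulated GEE test, with a sandwich variance and normal reference, also rejected about 1 to 3 points more often than the t-test. Part of this is small-sample liberality: its type I error was 0.028 against a nominal 0.025.

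**4. What covariates could add.** If 0.7 mm is unadjusted and covariates explain a share R² of patient-level variance, the residual SD is 0.7 × √(1 − R²). By exact t:

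- 44 per group: R² = 0 gives 85.5%; R² = 12% (SD 0.657) gives about 90%.
- 40 per group: 85% needs an SD of 0.671, so R² = 1 − (0.671/0.7)² ≈ 8%; 90% needs 0.624, so R² ≈ 20%. By normal approximation the figures are about 5% and 18%.

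An ANCOVA on patient means could use the same covariates.

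**The case against.** The strongest defence is that the planned GEE is not just a clustering device. Protocol 13 and the synopsis adjust it for baseline, and the SAP adds site and smoking. Moving from an unadjusted t-test to that model can raise power, and at 44 per group an R² of 0 to 12% spans almost exactly the stated range. This stands as a possibility. However, the documents do not say whether 0.7 mm is raw or already adjusted, and they state no R².

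A reader might infer three stronger things, none of which the documents support:

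- **That GEE cannot add power.** With a very low ICC and uneven site counts, weighting alone can add several points. The documents do not give the quantities needed to exclude this.
- **That the upper end needs zero dropout.** The primary analysis is ITT on all randomised subjects (SAP 4 and 8.3), and SAP 8.1.1 imputes the worst observation after withdrawal. About 50 per group are then analysed, for a nominal 90%. That figure assumes that imputation neither dilutes the treatment difference nor inflates the SD, which the plan does not address.
- **That 85 to 90% is an impossible figure.** It is reproducible without GEE at 44 to 50 per group. What lacks support is the reason given for it, and its use beside a 20% dropout rate.

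It is also fair to say that no analysis, alpha level or enrolment number depends on the sentence, and that the SAP's sizing text does not carry it.

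**Conclusion.** The point holds in limited form. The protocol attributes 85 to 90% power to GEE without an ICC, site count or R². Its own inputs give 81.6% (83.0% by normal approximation) with the 40 completers per group implied by its dropout rate, about 2 to 3 points below the bottom of the range. At the SAP's 10% dropout the figure is 86.4% (87.4%), inside the range without any help from GEE. Clustering is likely to contribute little; a material gain would come mainly from covariates.

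This rests on a difference of 0.5 mm, an SD of 0.7 mm for the patient mean, two-sided 0.025 and completers as the evaluable number. The ICC, site-count and R² ranges are assumptions. The related dropout step does not close at 20% either: 44 / 0.80 = 55 per group, against 50 enrolled, whereas 44 / 0.90 = 48.9, or 49, fits the SAP's rate.

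**What to change.** Delete the GEE sentence from Protocol 7.2 and the synopsis. Settle on one dropout rate across the protocol and SAP, and state power from the patient-level calculation at the resulting evaluable number: about 82 to 83% at 20% dropout, or about 86 to 87% at 10%. If the nominal 90% for 50 analysed per group is quoted, say that it assumes no dilution of the effect or inflation of the SD from worst-value imputation.

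Alternatively, if a gain from baseline PD, site and smoking is expected, say whether 0.7 mm is unadjusted, state the assumed R² with its source, and compute power from it. At 40 per group that means about 8% of patient-level variance for 85% power and about 20% for 90%.

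Either route changes wording only, with no change to the analysis or to enrolment. The cost is that, at 20% dropout and without a justified R², the protocol would have to state a power below 85%.

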## 7.3. Treatment Assignment

Group 1: ST266 dosed daily on Days 1-5, 8-12, 22, and 30 and then monthly for 7 months (Days 60, 90, 120, 150, 180, 210, and 240).

Group 2: ST266 dosed 2x/week (with at least one day between treatments) for the first 3 months and monthly for 5 months thereafter (Days 120, 150, 180, 210, and 240).

Group 3: Placebo dosed at the same frequency as Group 1.

## 7.4. Rescue Therapy

If at Day 90 or later a subject experiences progression of periodontitis in any tooth, rescue therapy will be provided. Progression of periodontitis is defined as an increase of 2 mm or more in PD or CAL from the baseline measurement (Goodson, 1982). Rescue therapy will consist of

the standard of care therapy at the tooth site where progression of periodontal disease occurred. Rescue therapy at the tooth site may occur immediately at the scheduled visit, or as soon as the investigator determines is reasonable to ensure the subject receives standard of care therapy.

Subjects that receive rescue therapy will continue to participate in all remaining study visits through study completion.

### **7.5. Criteria for Study Termination**

Safety assessments will be performed throughout the course of the study. Any potential safety issues that arise will be reviewed by the sponsor's Medical Monitor in consultation with the study investigators to identify the appropriate course of action. If the sponsor elects to terminate the study for any reason, the investigator will be responsible for notification of the institutional review board (IRB) and will withhold further treatment of study participants.

**Table 3: Study Design and Schedule of Assessments**

Evaluation	Treatment and Follow-up Period									
	Visit 1 Screening	Visit 2 Baseline (≤30 days from screening)	Visit 3/3b SRP (≤10 days from baseline)	Visit 4 Day 1 a (≤3 days from SRP)	Visit 5 Day 15 (±1 day)	Visit 6 Day 30 (±3 days)	Visit 7 Day 60 (±3 days)	Visit 8 Day 90 (±5 days)	Visit 9 Day 180 (±7 days)	Visit 10/EOS Day 270 (±7 days)
Informed Consent	X									
Pregnancy Test (female subjects)	X									X
Demographics	X									
Inclusion/Exclusion	X	X								
Dental History	X									
Medical History	X									
Vital Signs	X	X	X	X	X	X	X	X	X	X
Height and Weight	X b									X
Medical/Dental History Update g		X	X	X	X	X	X	X	X	X
Oral Exam	X	X	X	X	X	X	X	X	X	X
Randomization SRP d			X c X							
Full Mouth Plaque Index (FMPI)		X			X	X	X	X	X	X
Clinical Measurements (PD, CAL, BOP)	X				X	X	X	X	X	X
GCF Sampling		X			X			X e	X e	X
Serum Sampling		X			X			X	X	X
Microbial Sampling		X			X			X	X	X
Radiographs		X						X		X
General Labs	X f							X		X
Administration of Test Article				In-office treatments as scheduled in Figure 1						
Oral Hygiene Instruction g	X	X	X	X	X	X	X	X	X	X
Adverse Events g	X	X	X	X	X	X	X	X	X	X
Concomitant Medication g	X	X	X	X	X	X	X	X	X	X

BOP=bleeding on probing; CAL=clinical attachment level; EOS=end of study; FMPI=full-mouth plaque index; GCF=gingival crevicular fluid; HbA1c=glycated hemoglobin;

IWRS=interactive web response system; PD=pocket depth; SRP=scaling and root planing.

a The first in-office treatment may be performed on the same day as the last SRP visit. The last SRP may occur on Visit 3/3b, or as an Unscheduled Visit. The Unscheduled Visit may be combined with Visit 4. Product administration must occur within 3 days of the last SRP visit.

b Height is measured only at screening.

c Randomization occurs by IWRS after SRP has been completed.

d SRP may be initiated on the same day as the Baseline visit and may require more than one visit. Subjects with moderate to heavy deposits will typically have no more than two quadrants treated in a single SRP visit. Local anesthesia must be used for SRP.

[figure not shown]
e Sample is collected before treatment is applied.

f HbA1c is measured at screening only.

g Performed at each treatment visit, as well as at each evaluation visit.

**Figure 1: Dosing Schedules**

## Dosing Schedules

**Treatment Windows by Group (+/- Days)**

Groups	Visit Day									
	≤12	22	30	60	90	120	150	180	210	240
Groups 1, 3	N/A	3	3	3	5	7	7	7	7	7
Group 2	≤ 90					120	150	180	210	240
	N/A					7	7	7	7	7

## **8. SELECTION AND WITHDRAWAL OF SUBJECTS**

### **8.1. Subject Inclusion Criteria**

1. Provision of signed, written informed consent prior to participation in any study-related procedures.
2. Good general health as evidenced by the medical history.
3. Between 18 and 85 years of age at the time of informed consent signature.
4. Male or female.
5. Minimum of 18 teeth, excluding third molars.
6. Having moderate to severe periodontal disease according to American Academy of Periodontists (AAP) definition (at least 6 teeth with  $\geq 6$  mm PD and  $\geq 3$  mm CAL at baseline).
7. Having  $>30$  percent bleeding sites upon probing.
8. Willing to abstain from chewing gums and other mouth rinses for the study duration.
9. Ability and willingness to attend all study visits and comply with all study procedures and requirements.
10. Willingness to abstain from routine dental care.
11. For women with reproductive potential, willingness to use highly effective contraception (e.g., licensed hormonal contraception, intrauterine device, abstinence, or vasectomy in partner).

### **8.2. Subject Exclusion Criteria**

1. Presence of orthodontic appliances.
2. A soft or hard tissue tumor of the oral cavity.
3. Any dental condition that requires immediate treatment, such as carious lesions.
4. Participation in any other clinical study within 30 days of screening or during the study.
5. Pregnancy or lactation. If a subject meets this criterion, she may be rescreened for study participation when she no longer meets this criterion.
6. Antibiotic therapy within the last 30 days.
7. Chronic use ( $\geq 3$  times/week) of anti-inflammatory medications (e.g., non-steroidal anti-inflammatory drugs, steroids). Low-dose aspirin (less than 325 mg daily) is allowed.
8. Immunocompromised subjects.
9. Subjects with cancer or a history of cancer within the last 5 years of screening.

10. Any medical history or any concomitant medication that might affect the assessment of the study treatment or periodontal tissues, such as diabetes, nifedipine, phenytoin (Dilantin), or anticoagulant medications (e.g., warfarin [Coumadin] etc.).
11. Involvement in the planning or conduct of the study.
12. History of any clinically significant disease or disorder which, in the opinion of the investigator, may either put the subject at risk because of participation in the study, or interfere with interpretation of the subject's study results.
13. Previous randomization for treatment in the present study.

### **8.3. Re-screening of Subjects**

Subjects may be re-screened provided that they do not fail inclusion criterion 6 (having moderate to severe periodontal disease according to the AAP definition [at least 6 teeth with  $\geq 6$  mm PD and  $\geq 3$  mm CAL at baseline]).

### **8.4. Subject Withdrawal Criteria**

Subjects may voluntarily withdraw from the study, or be removed from the study at the discretion of the investigator or sponsor at any time. If such withdrawal occurs, or if the subject fails to return for visits, the investigator should determine the primary reason for a subject's premature withdrawal from the study and record the reason in the subject's study records.

All subjects prematurely discontinuing from the trial, regardless of cause, should be scheduled as soon as possible for a follow-up safety visit, which will include all assessments planned for Day 270 (end of study).

For subjects who are lost to follow-up (i.e., those subjects whose status is unclear because they fail to appear for study visits without stating an intention to withdraw), the investigator should document all steps taken to contact the subject, e.g., dates of telephone calls, registered letters, etc.

Subjects who are withdrawn from the study after beginning treatment will not be replaced.

---

 For the purposes of subject exclusion, *diabetes* is defined as any subject with (i) a history of type 1 or type 2 diabetes, (ii) prior or concomitant prescription of diabetes medications, or (iii) a laboratory test for glycated hemoglobin  $\geq 6.5$ .

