### 9.3. Treatment Compliance

Every treatment application of study drug will be performed in the dental clinic by the clinician/investigator (dental professional); therefore, non-compliance can be assessed easily by the investigator.

Treatments that are missed may be completed if done within the number of days indicated in [Table 5](#) from the original scheduled date.

Subjects who miss 20% or more of their prescribed treatments will be considered non-compliant and excluded from the per-protocol statistical analysis.

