5.2 Protocol Deviations

Major protocol deviation information will be maintained separately from the electronic CRF, and exports of these data will be delivered separately from the clinical datasets. A major deviation is one that may affect the outcome, analysis, or interpretation of the study. These deviations may include, but are not limited to, the following: Inclusion/exclusion criteria deviations, randomization deviations, and terminations for lack of compliance. Major protocol deviations will be identified by an expert committee prior to unblinding the study. Protocol deviations can be self-reported, recorded following interim monitoring visits, or following remote monitoring. For the per protocol analysis all subjects with minor deviations will be included. All subjects with major deviations will be reviewed as described above and will not be included in the per protocol analysis.

Subjects who miss 20% or more of their prescribed treatments will be considered non-compliant and will be excluded from the per-protocol statistical analysis.

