8. EFFICACY EVALUATION

8.1 Overview of Efficacy Analysis Issues

8.1.1 Handling of Dropouts or Missing Data

All reasonable efforts will be made to minimize missing data. However, there are two possibilities for data being missing. In one case, the measurement associated with an individual pocket may be missing at an evaluation. In this case, the worst previous value for this variable will be imputed for that tooth/pocket. Furthermore, the data from an entire patient may be missing because they withdrew before completing the study. For this imputation, an approach similar to that for each site will be employed. For visits that would follow a patient's premature discontinuation from the study, the worst observation associated with each individual pocket will be imputed for all subsequent visits for that patient and will thus also be carried forward for the 270-day evaluation. Subjects who drop out of the study will not be replaced.

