8.1.4 Assessment Time Windows

See Section 15.2 for the Schedule of Assessments. Assessments within the stated visit windows will be considered for analysis of the given time point. If multiple assessments occur within a visit window, the assessment occurring closest to the target day for the assessment will be used in the analysis. In the case of a tie, the worst record will be used.

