8.3 Analysis Methods

The Day 270 analyses will be independent of the Day 90 analyses. All primary and secondary efficacy analyses unless otherwise stated will be performed on the ITT population. Unblinding will be performed for the Primary and secondary analyses at Day 270.

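### Discretionary removal from the study can replace a measurable Day 270 outcome with a worst-value score in the ITT primary analysis

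*Protocol*

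**What the plan says.** Five provisions act together.

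- **Removal.** Protocol 8.4 allows subjects to leave voluntarily "or be removed from the study at the discretion of the investigator or sponsor at any time". The removal is from the study, not only from treatment. Anyone who leaves early should have the Day 270 assessments at a safety visit arranged promptly after discontinuation.
- **Non-compliance.** Under Protocol 9.3, a subject who misses 20% or more of the prescribed treatments "will be considered non-compliant and excluded from the per-protocol statistical analysis". SAP 5.2 and SAP 7 repeat this. SAP 5.2 also gives examples of what may count as a major deviation: "Inclusion/exclusion criteria deviations, randomization deviations, and terminations for lack of compliance".
- **Missing data.** For visits after premature discontinuation, SAP 8.1.1 states that "the worst observation associated with each individual pocket will be imputed for all subsequent visits for that patient", and this is carried to Day 270.
- **Analysis set and window.** SAP 8.3: "All primary and secondary efficacy analyses unless otherwise stated will be performed on the ITT population". SAP 8.1.4: "Assessments within the stated visit windows will be considered for analysis of the given time point". The schedule of events sets the Day 270 window at ±7 days.
- **Contrast.** Protocol 7.4: "Subjects that receive rescue therapy will continue to participate in all remaining study visits through study completion".

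**The concern.** An ITT analysis at Day 270 needs a Day 270 measurement from every randomized subject who can give one. A subject who has missed doses can still sit for a probing examination. Removing that subject from the study discards an obtainable primary outcome and substitutes a score that will usually show little or no improvement. The plan does not need the removal, because the per-protocol exclusion already deals with non-compliance, and rescued subjects are kept to the end.

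Two consequences follow. Substituted scores dilute any true effect even when removals are equal across arms. If removals differ by arm, they also bias the comparison. The Group 2 versus placebo contrast is the exposed one, because the two schedules differ. Groups 1 and 3 share a schedule, so visit burden gives no reason for an imbalance between them.

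**Working it through.** **1. The plan's own figure.** Inputs are a difference of 0.5 mm, SD 0.7 mm, 0.025 per comparison and 85% power (Protocol 7.2, SAP 2.6), with two-sided tests (SAP 3).

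n = 2(2.241 + 1.036)² × (0.7/0.5)² = 2 × 10.74 × 1.96 = 42.1, so 43 per group. A noncentral-t calculation gives 85.5% power at 44. The stated 44 is reproduced. With all 50 per arm measured, power is 90.8% (normal approximation).

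**2. Path of a removed subject.** The exit visit takes place soon after removal. Unless removal comes close to Day 270, that visit lies outside the ±7-day window. The SAP has no rule that treats the exit visit as Day 270, so the worst-value rule applies and the subject stays in the ITT set.

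**3. Treatment visits (Protocol 7.3).** Groups 1 and 3: 5 + 5 + 2 + 7 = 19. Group 2: 2 × 12 + 5 = 29 to 2 × 13 + 5 = 31.

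**4. Equal removal.** Assumptions not in the documents: the worst value equals baseline, so the change is 0, and the mean reduction *m* in measured placebo subjects is 1.0 to 2.0 mm. With a fraction *d* removed, arm mean = (1 − d) × mean reduction, and variance = (1 − d) × 0.7² + d(1 − d) × (mean reduction)².

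The difference is (1 − d) × 0.5, whatever *m* is.

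| d, both arms | Difference | Power at 50 per arm, m = 1.0 to 2.0 |
|---|---|---|
| 0 | 0.50 mm | 90.8% |
| 10% | 0.45 mm | 76% to 55% |
| 20% | 0.40 mm | 59% to 34% |

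Example, d = 10% and m = 1.0: the variances are 0.441 + 0.09 × 1.0² = 0.531 and 0.441 + 0.09 × 1.5² = 0.6435. SE = √((0.531 + 0.6435)/50) = 0.153, and 0.45/0.153 − 2.241 ≈ 0.69, so power is 76%.

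The 10% and 20% rows borrow the all-cause dropout figures of the SAP and the Protocol. They are upper bounds for discretionary removals alone.

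**5. Unequal removal, with no true effect.** The result depends on what triggers a termination.

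- *Constant risk per visit.* If 10% are removed over 19 visits, Group 2 loses 1 − 0.9^(29/19) = 14.9% to 1 − 0.9^(31/19) = 15.8%. The shift is 0.049 × 1.0 = 0.05 mm to 0.058 × 2.0 = 0.12 mm **against** Group 2.
- *Termination at the 20% threshold.* Let every visit be missed with probability 10% in all arms. The threshold is 4 of 19, 6 of 29 or 7 of 31 missed, and it is reached by 11.5%, 6.4% and 3.1% of subjects. If all of them were removed, Groups 1 and 3 would lose 5.1 to 8.4 points more. The shift is 0.051 × 1.0 = 0.05 mm to 0.084 × 2.0 = 0.17 mm **in favour of** Group 2.

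The sign changes with the trigger, and the documents do not state the trigger.

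**The case against.** The strongest reply is that nothing in the documents orders removal for missed doses. Protocol 8.4 is a general discretion clause. The 20% rule is stated three times, each time with a per-protocol consequence only. Protocol 12.1.6 and 12.1.6.2 let the Medical Monitor stop study drug without mentioning withdrawal from the study. SAP 5.2 classifies deviations and authorises nothing. Its terminations might be from treatment, since SAP 5.1 tabulates discontinuation of study treatment. Discretionary removals could be close to none, and much of the harm comes from the worst-value rule itself, which is a separate question.

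All of this stands as a limit on size. It does not close the gap: apart from the rescue provision, no passage says that a subject who stops dosing stays in follow-up, and Protocol 8.4 permits the opposite.

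A reader might also infer three stronger claims that the documents do not support.

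- *That the SAP expects such terminations.* It lists them only among things that may occur.
- *That removals will be most frequent in Group 2.* The visit counts make a difference plausible, and Protocol 13.2 ties dropout to the number of in-office treatments. But no per-arm figure is given, and step 5 shows that the order can reverse.
- *That the bias could reach half of the 0.5 mm target.* This needs 10 points of extra removals in Group 2 and an assumed 2.5 mm improvement (0.10 × 2.5 = 0.25 mm). The 10 points are the gap between the Protocol's 20% dropout and the completion above 90% in earlier studies. That gap is trial-wide and covers all causes, including voluntary withdrawal and loss to follow-up. The SAP's expected dropout of about 10% leaves little gap at all.

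**Conclusion.** The point holds as an inexpensive improvement, not as a demonstrated bias of known size. The plan permits avoidable loss of primary outcomes and then scores that loss at the worst value. Equal removal of 10% per arm would reduce 0.50 mm to 0.45 mm. Unequal removal would bias Group 2 versus placebo, with direction and amount undetermined.

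These figures rest on scoring removed subjects as no change. SAP 8.1.1 does not say whether the screening value counts as an observation. If only later values count, the dilution is smaller; if a later value is worse than screening, it is larger. The power figures and the shifts also need the assumed 1.0 to 2.0 mm reduction. The number of discretionary removals is unknown.

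**What to change.** - Amend Protocol 8.4 so that missed or stopped study treatment is not by itself a reason to end follow-up. Ask these subjects to attend the remaining scheduled evaluation visits, above all Day 270. The exceptions are withdrawn consent, loss to follow-up, or another protocol provision that requires exit. Reconcile the text with the pregnancy withdrawal in Protocol 12.5.4.
- State in the SAP that measured Day 270 values from these subjects enter the ITT analysis. SAP 8.1.1 would then apply only to those who have actually left.
- In SAP 5.1, record discontinuation of treatment and discontinuation of the study separately.

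The examples in SAP 5.2 can stay, since deleting a classification changes no conduct. When dosing stops is not affected.

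Cost: a protocol amendment with IRB approval before implementation, a short SAP revision, and effort to retain subjects who have stopped dosing. The visits are already scheduled. Enrolment was under way when these versions were written, so the benefit is limited to subjects still in follow-up.
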